9.2. Sample Size Determination

The primary endpoint in this study is the PASI 90 response rate at Week 16. Assuming a PASI 90 response rate as 5% for the placebo group, and placebo corrected effect 35% or greater for one of the treatment groups, a total of N=128 completers are needed to ensure at least 90% power for the lower doses due to Bonferroni multiplicity adjustment with 1-sided type-I error rate of 5% and 2:1:1:2:2 allocation ratio of placebo, 50 mg, 100 mg, 200 mg, and 400 mg. The total sample size includes a sample size of 32 completers per arm for placebo, 200 mg and 400 mg, and 16 completers per arm for 50 mg and 100 mg. Accounting for a 20% chance of drop out, approximately a total of 160 participants will be enrolled in this study.

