9.4.1. Efficacy Analyses

Endpoint	Statistical Analysis Methods
Primary and key secondary: PASI 90 and PASI 75 at Week 16	A landmark analysis of the composite endpoint; achieving a PASI 90 response (a score of 90% improvement from Baseline) without prohibited medication, while remaining on study and providing data. The analysis will use the mITT analysis set. Based on the definition of the composite endpoint all participants in the mITT set will have a response for all visits (ie, there is no missing data). The proportions responding and the risk difference between treated arms and their corresponding placebo arm will be analyzed using an unconditional exact method: risk differences and corresponding 2-sided unconditional exact 90% confidence intervals will be computed using the Chan and Zhang (1999) method. Multiplicity adjustment will be utilized; details of multiplicity adjustment will be provided in the SAP.

Other continuous secondary endpoints at time points specified in the [Schedule of Activities](#) including; absolute PASI, change from baseline PASI, percent change from baseline PASI, absolute and change from baseline Itch Severity Score, absolute and change from baseline Psoriasis Symptom Inventory will be analyzed as described for the E2 estimand along with descriptive statistics and possibly graphical displays. No adjustments for multiplicity will be made for these endpoints.

Other binary secondary endpoints at time points specified in the [Schedule of Activities](#) including, PASI 50, PASI 100, PGA of clear or almost clear and proportions of participants achieving a Psoriasis Symptom Inventory Score of 0 or 1 will be analyzed as described for the primary estimand along with descriptive statistics and possibly graphical displays. No adjustments for multiplicity will be made for these endpoints.

CCI [REDACTED]

All endpoints in Extension Treatment Period will be analyzed with descriptive statistics and graphical displays when appropriate. Details of the analyses of the Investigational Treatment Period and Extension Treatment Period will be included in the Statistical Analysis Plan (SAP).

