
To compare the efficacy of multiple dose levels of PF-06826647 versus placebo on the proportion of participants with moderate to severe plaque psoriasis achieving PASI 50 and PASI 100.
	
 • Proportion of participants achieving PASI 50 (50% or greater improvement from Baseline), PASI 100 (100% from Baseline) at time points specified in the SoA. 	

To compare the efficacy of multiple dose levels of PF-06826647 versus placebo on PGA and PASI scores in participants with moderate to severe plaque psoriasis.
	
 • Change from baseline and percent change from baseline in PASI scores at time points specified in the SoA. 	
Estimand E2:
 
This estimand is intended to provide a population level estimate of the treatment effect of the IP alone on a continuous endpoint; without the benefit of additional prohibited medications, regardless of participant's compliance with the IP dosing.
 
Population: Participants with moderate to severe plaque psoriasis as defined by the inclusion and exclusion without the benefit of additional prohibited medications regardless of compliance.
 
Intercurrent Events: A) Prohibited medication – all scores after participants receive prohibited medication will be omitted from the analysis and treated as missing scores. Missing scores will be imputed based on the assumption that participants do not benefit from the IP treatment. B) Withdrawal and all other events leading to missing data will be treated similarly as in A). C) Inadequate compliance – participants data will be used as recorded.

Objectives	Endpoints	Estimands
To compare the effect of multiple dose levels of PF-06822647 versus placebo in Peak-Pruritus Numerical Rating Scale score in participants with moderate to severe plaque psoriasis.	
 • Absolute score and change from baseline in Peak-Pruritus Numerical Rating Scale score at time points specified in the SoA. 	
Population level summary:
 
The mean difference between treated and placebo arms of the change from baseline PASI score.
 
All continuous endpoint, when appropriate will be analyzed descriptively and using estimand E2 described above when appropriate.

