5.2. General Methods

5.2.1. Analyses for Binary Endpoints

Landmark (cross-sectional) analyses of key binary endpoints will calculate and test for risk differences using the method of (Chan and Zhang 1999).² Covariates will not be included in the primary analyses. Risk differences and 90% confidence intervals will be presented.

For all key binary endpoints such as PASI75, PASI90 and PGA scores etc that are measured repeatedly over time, will be analyzed using generalized linear mixed effect model (GLMM) with treatment group (defined as factor variable), visit, treatment group by visit interaction and subjects as the random effect. An unstructured covariance matrix will be used to fit such model. In case, if the model fails to converge, a covariance structure such as compound symmetry or autoregressive model may be used. Bayesian information criterion (BIC) will be used to assess the goodness of fit of the models. The model with the smallest BIC will be selected for inference. P-values and inference for relative risks between treatments will be provided based on the link function of logit.

For all binary endpoints, a summary based on the mITT Observed Efficacy Set of the number of subjects in each category based on observed cases in each treatment arm at each time point will be produced and the response rate will also be plotted against time, by treatment group.

Exploratory categorical analyses that include or assess the effects of covariates may be done on an exploratory basis. Exploratory longitudinal analyses may also be performed including appropriate covariates of interest.

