5.2.2. Analyses for Continuous Endpoints

Landmark (cross-sectional) analysis of key continuous endpoints will use analysis of covariance (ANCOVA). The ANCOVA model will include terms for treatment arm and baseline score of the dependent variable. Least-squares means at the mean overall baseline score will be presented along with 90% confidence intervals.

Mixed model repeated measures (MMRM) models will be used. The fixed effects of treatment, visit (Weeks 1, 2, 4, 6, 8, 12 and 16), and treatment-by-visit interaction will be included. Visit will be modeled as a categorical covariate. Unstructured covariance matrix will be assumed for the model errors. Compound symmetry covariance matrix will be used if the model with unstructured covariance doesn't converge.

When modeling the change from baseline values, the variable for visit will start with the first post-baseline visit, and the actual baseline value will be included as a covariate. At each visit, estimates of least square mean (LSM) values and the LSM differences between the PF-06826647 treated groups and placebo group will be derived from the model. The corresponding p-values and 90% confidence intervals will also be derived from the model.

Unless stated otherwise, descriptive summary statistics for all continuous variables will be presented on mITT Observed Efficacy Set by treatment group and will include the following: n, mean, median, standard deviation, minimum and maximum.

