6.2.4. Secondary Endpoints: Continuous Data

Analyses of all continuous endpoints such as PASI, CCI PP-NRS, PSI, CCI etc for their percentage change or absolute change from baseline or absolute values:

- Estimand strategy: Primarily this estimand is intended to provide an estimate of the treatment effect in the population level assuming missing data are either MCAS (Missing Completely at Random) or MAR (Missing at Random). Applicable statistics will be calculated at time points specified in the SoA.
- Population: mITT.
- Analysis methodology: MMRM and descriptive statistics.
- Missing Data: Observed Data.

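### As written, the SAP's MMRM has no baseline term for absolute scores and is unclear for percent change, and the supplementary GLMM has no baseline term at all

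*SAP*

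**What the plan says.** SAP 5.2.2 describes two continuous models. The landmark ANCOVA has treatment arm and the baseline score of the dependent variable, with no restriction to change scores. For the MMRM the text reads: "The fixed effects of treatment, visit (Weeks 1, 2, 4, 6, 8, 12 and 16), and treatment-by-visit interaction will be included". Baseline enters one paragraph later, under a condition: "When modeling the change from baseline values, the variable for visit will start with the first post-baseline visit", with the baseline value then added as a covariate. SAP 6.2.4 applies the MMRM to the continuous endpoints for their "percentage change or absolute change from baseline or absolute values".

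The endpoint lists disagree about absolute scores:
- SAP 3.1.2 keeps only change from baseline for PP-NRS and PSI, and only change and percent change for continuous PASI. The SAP version history shows that absolute PP-NRS and PSI were dropped on purpose in version 3.0.
- SAP 2.1 still lists "Absolute score and change from baseline in Peak-Pruritus Numerical Rating Scale score at time points specified in the SoA", with a matching line for PSI.
- Protocol 9.4.1 still names "absolute PASI, change from baseline PASI, percent change from baseline PASI" among the continuous secondary endpoints.

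For repeated binary endpoints, SAP 5.2.1 specifies a GLMM with treatment group, visit, "treatment group by visit interaction and subjects as the random effect". The Appendix 5 code has the same three fixed terms and no baseline. Longitudinal models with covariates are optional and exploratory. SAP Appendix 1 labels the GLMM sensitivity/supplementary, on observed data. The main binary analysis is the Chan and Zhang risk difference, and 5.2.1 excludes covariates from the primary analyses.

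**The concern.** Baseline PASI, PGA, PSI and PP-NRS are all collected on Day 1, so leaving them out of a model saves nothing. A programmer who follows 6.2.4 literally would fit an absolute-score MMRM without baseline. Part of any chance baseline imbalance, set by the regression slope, would then pass into the treatment contrast. The same data would yield one difference and p-value for the change score and another for the absolute score. For PP-NRS and PSI scores the MMRM is the only inferential model in 6.2.4 and Appendix 1, so the ANCOVA does not settle the matter for them.

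In the GLMM, PASI 50/75/90/100 are already defined relative to baseline, but PGA 0/1 and PSI ≤8 (every item 0 or 1) are absolute thresholds. These analyses use observed data under a stated MCAR or MAR assumption. If dropout depends on baseline severity, a model without baseline makes that assumption harder to defend.

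**Working it through.** The plan states no precision figure for these analyses, so there is none to reproduce.

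**Inputs.** Arm sizes are 40 (placebo, 200 mg, 400 mg) and 20 (50 mg, 100 mg), from Protocol 4.1. These match Protocol 9.2: 32/0.8 = 40 and 16/0.8 = 20. Response rates are from Protocol 9.2, "Assuming a PASI 90 response rate as 5% for the placebo group, and placebo corrected effect 35% or greater", so 5% against 40%. The documents give no baseline SD, no r and no association of baseline with response. Those are assumptions, shown as ranges.

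**1. Absolute score without baseline.** At one visit with complete data, the variance of the difference is σ²(1/n₁ + 1/n₀) unadjusted and σ²(1 − r²)(1/n₁ + 1/n₀) adjusted. The ratio of interval widths is 1/√(1 − r²):

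| r | 0.1 | 0.3 | 0.5 | 0.7 |
|---|---|---|---|---|
| unadjusted / adjusted width | 1.005 | 1.048 | 1.155 | 1.400 |

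**2. Chance imbalance.** With an assumed baseline PASI SD of 7, the baseline difference of a 20-participant arm from placebo has SD 7 × √(1/20 + 1/40) = 1.92 points.

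**3. Absolute against change score.** If Y = treatment terms + βB + error, then Y − B = the same treatment terms + (β − 1)B + error. Only the baseline coefficient changes. A simulated check with 40 per arm gave −7.544 (SE 1.085) for both outcomes with baseline in the model. The absolute score without baseline gave −7.425 (SE 1.167), an SE 1.167/1.085 = 1.08 times as large.

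**4. GLMM, logit link, one visit, 5% against 40%.** Without baseline, the log-odds ratio is ln(0.40/0.60) − ln(0.05/0.95) = 2.539. Its SE at 40 per arm is √(1/(40×0.05×0.95) + 1/(40×0.40×0.60)) = 0.794, so z = 3.20. Adding a standardised baseline covariate with an assumed log-odds ratio γ per SD, from the expected Fisher information:

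| γ | log-OR | SE | SE change | z | unadjusted risk-difference interval wider by |
|---|---|---|---|---|---|
| 0.3 | 2.570 | 0.799 | +0.7% | 3.22 | 0.6% |
| 0.5 | 2.626 | 0.810 | +2.0% | 3.24 | 1.7% |
| 1.0 | 2.882 | 0.863 | +8.7% | 3.34 | 5.9% |

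With 40 against 20, z moves from 2.96 to 2.97, 2.99 and 3.02, and the last column becomes 0.8%, 2.1% and 7.1%.

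**5. Dropout related to baseline (all rates assumed).** Suppose 30% have baseline PGA 4, PGA 0/1 response is 55% (baseline 3) or 27% (baseline 4), and dropout is 10% or 40%. The true rate is 0.7×0.55 + 0.3×0.27 = 46.6%. The observed rate is (0.63×0.55 + 0.18×0.27)/0.81 = 48.8%. This shows only the mechanism. It is a raw rate in one arm, neither a GLMM estimate nor a treatment contrast.

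**6. Sparse cells.** Protocol 4.3 projects PASI 90 rates of 3% (50 mg) and 13% (100 mg). In arms of 20 that is 0.6 and 2.6 expected responders.

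**The case against.** The strongest reply is that little is lost. The ANCOVA, which is the main analysis of continuous PASI, includes baseline. SAP 3.1.2 no longer has absolute scores as endpoints, so what remains is leftover wording. By step 3, the planned change-score MMRM with baseline already delivers the contrast that an adjusted absolute-score model would give. All of this stands. It limits the point to an inconsistent specification and a redundant, less precise contrast that could still be produced. It does not remove the point, because 6.2.4 is current text and names absolute values.

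Three stronger readings are tempting, and the documents do not support them:
- A reader might infer that the SAP adjusts for baseline only in change-score models. The ANCOVA sentence in 5.2.2 contradicts that.
- A reader might infer that omitting baseline widens the GLMM intervals. On the logit scale the direction is the opposite: adjustment moves the log-odds ratio away from zero and raises its SE, with a small gain in z. Intervals narrow only for standardised risk differences.
- A reader might infer that the main results are at risk. The primary Chan and Zhang analysis is unadjusted by stated choice, and the GLMM is supplementary.

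It is also fair that entry requires PGA 3 or 4. Baseline PGA then has two levels, and PGA 0/1 already implies an improvement of at least 2 points. Baseline 3 against 4 may still be prognostic. An extra term in a model that already has a convergence fallback is not free where responders are few.

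**Conclusion.** The point holds for the MMRM specification and, with less weight, for the GLMM. An absolute-score MMRM fitted as written would have intervals about 5% wider at r = 0.3 and 15% wider at r = 0.5, and would disagree with the change-score model. Whether baseline enters the percent-change MMRM cannot be settled from the text, although the percent-change ANCOVA has it.

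For the GLMM, adding baseline would bring a little power and risk-difference intervals about 1–6% narrower (up to about 7% against a 20-participant arm), plus a more defensible MAR assumption for PGA 0/1 and PSI ≤8.

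These sizes rest on assumed correlations and associations, on single-visit calculations and, for the GLMM, on the protocol's 5% and 40% rates. The 1/√(1 − r²) figure assumes a baseline slope specific to the visit; one slope shared by all visits may recover somewhat less. No primary inference changes.

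**What to change.** 1. Reconcile SAP 2.1, SAP 6.2.4 and Protocol 9.4.1 with SAP 3.1.2 on whether absolute scores are modelled or only summarised. In SAP 5.2.2, state that the baseline score is a covariate in every MMRM, including percent change and any absolute-value model, ideally with a baseline-by-visit term. The cost is a few sentences and one covariate.
2. At lower priority, add the baseline value of the underlying scale (PASI, PGA or PSI) to the GLMM in SAP 5.2.1 and Appendix 5. Report Week 16 risks and risk differences standardised over the observed baseline distribution. The cost is an odds ratio that becomes conditional on baseline, a few more lines of code, and possible convergence problems for PASI 90 in the 50 mg and 100 mg arms. State in advance what is reported if the adjusted model does not converge. Pre-specifying the covariate also removes the discretion that the optional exploratory models now leave open.

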6.2.3.1. Main analysis

- Estimand strategy: Secondary Estimand ([Section 2.1.2](#)) use a composite endpoint strategy. This estimand is intended to provide an estimate of the treatment effect in the absence of prohibited medication use in a population that may or may not be fully compliant with the treatment.

- Analysis set: mITT (Section 4.1) using data prepared in the description of the Secondary Estimand Continuous Endpoint Set.
- Analysis methodology: ANCOVA model with treatments arms and baseline score as dependent variable.
- Intercurrent events and missing data: These have been accounted for in the estimand (Section 2.1.2) and missing data will be imputed using a contro based imputation method (Section 5.3).
- Mean difference of change/percent change from baseline PASI score and 90% confidence intervals will be presented.

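### If the unstructured MMRM does not converge, the SAP allows only compound symmetry, which could misstate visit-specific standard errors in either direction, mainly for PP-NRS and PSI

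*SAP*

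**What the plan says.** SAP Section 5.2.2 starts from an unstructured matrix: "Unstructured covariance matrix will be assumed for the model errors". The mean model is full: "The fixed effects of treatment, visit (Weeks 1, 2, 4, 6, 8, 12 and 16), and treatment-by-visit interaction will be included", and for change scores "the actual baseline value will be included as a covariate". Least-squares means and differences from placebo are estimated at each visit, and "The corresponding p-values and 90% confidence intervals will also be derived from the model". The only fallback is this: "Compound symmetry covariance matrix will be used if the model with unstructured covariance" fails to converge. No intermediate structure, information-criterion choice or robust standard error is mentioned for this model. The rule for the binary mixed model in SAP Section 5.2.1 is broader: it allows compound symmetry or an autoregressive structure and selects by BIC.

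The role of the MMRM differs by endpoint:

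- **PASI change and percent change at Week 16.** The main analysis is ANCOVA after control-based multiple imputation (SAP Section 6.2.3.1). The MMRM is sensitivity/supplementary (SAP Section 6.2.3.2).
- **Continuous PP-NRS and PSI.** SAP Section 6.2.4, whose scope opens with "Analyses of all continuous endpoints such as PASI", gives only "Analysis methodology: MMRM and descriptive statistics". Appendix 1 labels this sensitivity/supplementary but lists no main model for these two endpoints.

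**The concern.** Moving from unstructured to compound symmetry removes every visit-specific variance in one step. With seven visits, an unstructured matrix has 7 × 8 / 2 = 28 parameters and compound symmetry has 2. The fallback model then attaches an average-visit variance to every visit. A contrast at a visit with above-average residual variance gets a standard error that is too small, and one at a visit with below-average variance gets one that is too large.

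The MMRM's output is a set of per-visit comparisons, so this error goes directly into the reported results. For PASI change at Week 16 there is a separate main analysis to rely on. For continuous PP-NRS and PSI, which the protocol lists as secondary endpoints, the MMRM is the only source of model-based inference that the SAP provides.

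**Working it through.** **Inputs from the documents.** There are seven post-baseline visits for PASI (SAP Section 5.2.2). PP-NRS and PSI have six, because the Schedule of Activities has no Week 6 assessment for them; their unstructured matrix has 6 × 7 / 2 = 21 parameters. Arms are 40/20/20/40/40 with 20% dropout (Protocol Section 9.2). Neither document states an SD or correlation by visit for any continuous endpoint, so there is no figure in the plan to reproduce and the SD patterns below are assumptions.

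**Formula.** With complete data and a treatment-by-visit mean model, the Week 16 contrast is essentially a difference of arm means. Its true variance is proportional to the Week 16 variance, while compound symmetry substitutes the average variance over visits. Hence

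r = model SE / true SE = √(mean of visit variances / Week 16 variance),

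90% interval coverage = 2Φ(1.645 r) − 1, and one-sided error at nominal 5% = 1 − Φ(1.645 r).

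**One case in full.** SDs 4, 4.5, 5, 5.5, 6, 6.5, 7 have squares summing to 218.75, with mean 31.25. Then r = √(31.25 / 49) = 0.799, and coverage is 2Φ(1.314) − 1 = 0.81.

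**All patterns** (SDs evenly spaced over seven visits unless listed):

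| Assumed residual SD, Week 1 to Week 16 | Mean variance | Week 16 variance | r | 90% CI coverage | One-sided error |
|---|---|---|---|---|---|
| Rising 3 to 9 | 40.00 | 81 | 0.70 | 75% | 12% |
| Rising 4 to 7 | 31.25 | 49 | 0.80 | 81% | 9% |
| Rising 5 to 8 | 43.25 | 64 | 0.82 | 82% | 9% |
| Rising 6 to 7 | 42.36 | 49 | 0.93 | 87% | 6% |
| Flat at 6 | 36.00 | 36 | 1.00 | 90% | 5% |
| 3, 4.5, 6, 7, 7, 6, 5 | 32.04 | 25 | 1.13 | 94% | 3% |
| Falling 8 to 5 | 43.25 | 25 | 1.31 | 97% | 1.5% |

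**Six visits.** Dropping Week 6 from the 4-to-7 pattern removes 5.5² = 30.25. The mean becomes 188.5 / 6 = 31.42 and r = √(31.42 / 49) = 0.801, so the result carries over to PP-NRS and PSI. Only the ratio of SDs matters: 2 to 3.5 gives the same r as 4 to 7.

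**Simulation check.** A REML compound-symmetry fit was simulated with treatment-by-visit and baseline terms, the planned arm sizes and 20% monotone dropout. There were 600 replicates per scenario, comparing 400 mg with placebo at Week 16. Within-subject correlation was either exchangeable at 0.6 or AR(1) at 0.85. The ratios agree with the closed form:

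| Pattern | Simulated r | Simulated one-sided error |
|---|---|---|
| Rising 3 to 9 | 0.67–0.68 | 13–14% |
| Rising 5 to 8 | 0.79–0.82 | 9–11% |
| Flat at 6 | 0.95–1.02 | 5.5–6.7% |
| Rise then fall | 1.08–1.12 | about 4% |
| Falling 8 to 5 | 1.28–1.31 | 1.5–1.7% |

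Dropout was simulated as unrelated to outcome, so this checks standard errors only and not any shift in the estimates.

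**The case against.** A reader might infer that compound symmetry would make the Week 16 results anti-conservative. The argument would be that change scores are tightly grouped at Week 1 and spread out as responders and non-responders separate. That is plausible: the protocol projects 47% PASI 90 at 200 mg, which implies a mixed arm. But the documents do not establish it. They give no visit-specific SDs, and the same section of the protocol (4.3) projects 83% PASI 90 at 400 mg, where scores could bunch near zero and variance could shrink by Week 16. Divergence between arm means does not count either, because treatment-by-visit absorbs it; only spread within arms matters. The direction is therefore open.

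The consequence is also limited, and these limits stand:

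- The fallback applies only on non-convergence, and nothing in the documents suggests that 28 or 21 covariance parameters with about 160 participants would fail.
- Non-convergence does not imply rising variance; understated errors need both.
- SAP Section 5.1 places formal inference on PASI 90 at Week 16, analysed by the Chan and Zhang method. Neither that analysis nor the PASI ANCOVA fits a covariance across visits.
- A reader might take the MMRM as the confirmatory analysis of PP-NRS and PSI because no other model is listed. Appendix 1 labels it sensitivity/supplementary, and Protocol Section 9.4.1 makes no multiplicity adjustment for the other continuous secondary endpoints.
- The rule is prespecified and deterministic, so it is not a gap or a contradiction.

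None of this defends compound symmetry as the only alternative. It gives correct per-visit standard errors only if the variance is flat, whereas a structure with visit-specific variances can accommodate a rise or a fall.

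**Conclusion.** The point holds as a minor one. If the unstructured MMRM fails to converge, the prescribed fallback could misstate per-visit standard errors, p-values and 90% intervals, with the direction set by how residual variance changes over visits. Over the assumed patterns, the Week 16 standard error ranges from about 30% too small (SD 3 to 9) to about 31% too large (SD 8 to 5), and is about right when variance is flat. These figures rest on assumed SDs and are not estimates for this trial. The documents do not support saying that the standard error will be understated. The practical reach is continuous PP-NRS and PSI, and PASI by visit as a supplementary analysis. The primary PASI 90 result and the main PASI ANCOVA do not change.

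**What to change.** Replace the fallback sentence in SAP Section 5.2.2 with an ordered list that keeps visit-specific variances: heterogeneous Toeplitz, then heterogeneous AR(1), then heterogeneous compound symmetry. Use the first that converges, and plain compound symmetry only as a last resort. Fix the order before unblinding so that the choice cannot depend on the results.

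Sandwich standard errors are optional. Uncorrected ones tend to be too small in small groups, and the 50 mg and 100 mg arms have 20 participants each (16 expected completers), so a small-sample correction should be specified if they are used.

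The cost is one SAP sentence and a few lines of code. There is no effect on sample size, data collection or the primary analysis.
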